10.4 Sample Size and Power Calculations

The sample size of 40 evaluable couples, with 20 couples in each group (Single Dose /BAT Cohort and Multiple Dose Cohort), was determined with respect to the primary PK endpoints. Details are provided in the section below. Given this sample size, power calculations are also provided for the PD primary endpoint.

10.4.1 Pharmacokinetic Endpoints

Sample size/power formulas for a one-sample, paired t-test, can be used to compute sample size/power. For the primary PK endpoint to assess the impact of coitus on the PK of tenofovir following a single dose and BAT regimen (Group 1), and separately if indicated, following seven daily doses (Group 2), we use data from two studies:

- 1) a 14-day tenofovir gel study in which CVL TFV levels and anti-HIV-1 activity were measured on Days 3 and 7,¹⁷ and
- 2) a post-coital study by Keller, et al.⁵ which addressed the impact of coitus on the PK of PRO 2000 Gel following a single dose of gel.

From these studies, we estimate the standard deviation of CVL tenofovir data after daily dosing at Days 3 and 7, and the standard deviation for the percentage difference in drug concentration (DC) levels between gel use alone and gel use prior to coitus. We make the assumption that the standard deviation for this percentage difference will be similar for tenofovir 1% gel as it was for PRO 2000 Gel. We also assume that the standard deviation will be similar for the percentage difference due to coitus following seven daily doses as it was for coitus following a single dose.

From the tenofovir 14-day study, we estimated the coefficient of variation (CV) of the gel-only DC levels from CVL at Days 3 and 7 to be 1.2 and 1.1, respectively. From the PRO 2000 Gel study we estimated the mean (SD) percentage change in CVL drug concentration due to the impact of coitus ($1 - ([\text{gel and sex DC}] / [\text{gel-only DC}]) \times 100\%$ for each couple). The mean percentage change was 68% and the standard deviation was 31% (CV of $0.31/0.68=0.5$). The gel/sex and gel-only PRO 2000 DC levels yielded CVs of 1.1 and 0.9, respectively. The tenofovir 14-day study produced mean tenofovir DC levels on the same order of magnitude (ng/mL) as seen with the PRO 2000 DC levels in the PRO 2000 post-coital study. For the MTN-011 study, we assume a conservative CV of 1.5 for the mean percentage change due to the impact of coitus. It is estimated that a 25% difference in drug concentration levels due to coitus would be biologically important to be able to detect. Thus, a CV of 1.5 translates to a standard deviation of 37.5%, and with a sample size of 20 couples, this study is designed with 80% power to detect at least a 25% difference in drug concentration levels due to coitus.

Based on a one-sample, paired t-test, the table below summarizes the power available to detect various percentage differences in drug concentration levels due to coitus for a sample size of 20 couples. The table also provides this information for various estimates of the standard deviation (Sigma) in the case that our assumptions are not met.

Table 18: Power for Minimum Detectable Differences in Drug Concentration Levels for Within Group Comparisons of Gel Use vs. Gel Use Prior to Coitus (N=20)

Minimum detectable difference in drug concentration levels	Sigma (CV)				
	0.25 (1.0)	0.3125 (1.25)	0.375 (1.5)	0.4375 (1.75)	0.5 (2.0)
5%	0.136	0.104	0.088	0.077	0.071
10%	0.397	0.274	0.205	0.163	0.136
15%	0.721	0.531	0.397	0.308	0.247
20%	0.924	0.775	0.619	0.492	0.397
25%	0.989	0.924	0.807	0.679	0.565
30%	>0.999	0.982	0.924	0.829	0.721
35%	>0.999	0.997	0.977	0.924	0.844
40%	>0.999	>0.999	0.995	0.972	0.924
45%	>0.999	>0.999	>0.999	0.992	0.968
50%	>0.999	>0.999	>0.999	0.998	0.989

10.4.2 Pharmacodynamic Endpoint

In the table below, a power calculation is provided for the pharmacodynamics primary endpoint to assess the impact of coitus (and semen) on PD of luminal drug by measuring the anti-HIV-1 activity in CVL samples.

In the tenofovir 14-day study, the standard deviation of the percent inhibition of HIV-1 activity among participants in the tenofovir arm at Days 3 and 7 was 21.1% and 22.9%, respectively.²⁵ In comparison, we estimate the standard deviation of the percent inhibition of HIV-1 from the Keller PRO 2000 gel study to be 17.2% for the difference between the post-coital, post-gel visit and the post-gel visit, which is similar to the variability in the tenofovir 14-day study at Days 3 and 7 post-gel.⁵ Assuming a standard deviation of 20.0% for the absolute difference in percent inhibition of HIV-1 between the visits where the female participants dose with gel and engage in coitus vs. the visits where female participants dose with gel and do not engage in coitus. In this study, the table below provides estimates of the power available, based on a one-sample, paired t-test, to detect various minimum detectable absolute differences in percent inhibition of HIV-1.

Table 19: Power for Minimum Detectable Absolute Differences in Percent Inhibition of HIV-1

Minimum detectable absolute difference in % inhibition of HIV-1	Power
2	0.071
4	0.136
6	0.247
8	0.397
10	0.565
12	0.721
14	0.844
16	0.924
18	0.968
20	0.989

This study has moderate (56%) power to detect an absolute difference of at least 10% inhibition of HIV-1 between the visits where the female participants dose with gel and engage in coitus vs. the visits where female participants dose with gel and do not engage in coitus.

10.5 Participant Accrual, Follow-up and Retention

The accrual and follow-up period will be 6-12 months. More than 20 couples may be enrolled into each group to reach the target of 20 evaluable couples in each group.

A couple is considered evaluable if ALL of the following have been achieved:

- The primary pharmacokinetic endpoints (tenofovir levels from cervicovaginal lavage (CVL) and vaginal/cervical tissue biopsies) are provided at both the visits where the female participants dose with gel and engage in coitus and the visits where female participants dose with gel and do not engage in coitus, and
- At each Gel/Sex Visit, the couple has completed coitus, and
- In Group 2, gel has been used daily at least 5 of the 7 days prior to the study visits

Couples in Group 1 will be followed for approximately 8 weeks and couples in Group 2 will be followed for approximately 14 weeks.

As stated above in the definition of an evaluable couple, to adequately assess the primary PK objective of this study, it is important for each couple to provide complete data throughout follow-up. Thus, target retention should be set at 100%. Once a couple is enrolled in the study, the study site will make every reasonable effort to retain the couple for the entire study period so that they are evaluable.

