At Visit 6 (Provision of Product) while in the clinic, the female participant will vaginally administer the content of one applicator of tenofovir 1% gel. For the next six consecutive days she will vaginally insert the content of one applicator of tenofovir 1% gel daily at home (i.e., doses 2-7). Doses should be inserted at approximately the same time each day. Approximately 72 hours after the administration of the last vaginal dose, couples will return to the clinic for Visit 7a (Gel -72/Coitus). Following a minimum washout period of 20 days to allow for clearance of any residual drug and to provide time for the participant's menstrual period, the female participant will return to the clinic for Visit 8 (Provision of Product) and insert into the vagina the content of one applicator of tenofovir 1% gel. For the next six consecutive days she will insert into the vagina the content of one applicator of tenofovir 1% gel daily at home (i.e., doses 2-7). Doses should be inserted at approximately the same time each day. The final dose of gel should be administered approximately 72 hours prior to Visit 9/Final (Sampling).

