7.4 Group 2 (Multiple Dose Cohort)- Screening Visit (Visit 1)

A Screening Visit may take place up to 30 days prior to the Enrollment Visit. Multiple visits may be conducted to complete all required screening procedures, if necessary. Written informed consent for screening will be obtained before any screening procedures are initiated. Both the female and the male must meet the eligibility requirements for the couple to be eligible. For participants who do not meet the eligibility criteria (e.g., STI or HIV-positive, self-reported non-monogamy, etc.), screening will be discontinued for the couple once ineligibility is determined.

All test results will be provided to an individual participant in a private room to ensure participant confidentiality. If a participant is found to be ineligible based upon STI or HIV status study staff will not inform the infected participant's partner. Participants may choose to disclose this information on their own. Study staff will comply with local requirements to report communicable diseases including HIV-1 identified among study participants to health authorities.

In addition, if one partner admits to non-monogamy, study staff will inform the couple that they are ineligible for the study; however non-monogamy will not be disclosed to the couple as the reason for ineligibility.

All individuals who come to the clinic for Screening will be provided counseling regarding HIV/STI prevention, see Table 11. Participants will be informed that condoms are the only known way to prevent HIV and other STIs.

Note: Participants may rescreen a total of one time; however both the female and male participants must meet the eligibility requirements at the time of the screening.

Table 10: Group 2- Multiple Dose Cohort Study Visit Schedule

Group 2- Multiple Dose Cohort				
Gel	Visit	Visit Name	Targeted Visit Schedule	Coitus
	1 ♂♀	Screening (Baseline CVL)		
	2 ♂♀	Enrollment- Provision of Study Product	To occur ~2-3 days following the final day of the female participant's period*	
-1 hr	3a ♂♀	Gel -1/Coitus	To occur 6 days after Visit 2	X
	3b ♀	Post-Coital Sampling	To occur ~2 hrs after coitus	
	4 ♀	Provision of Study Product	To occur after a min. 20 day washout period	
	5 ♀	Sampling	To occur at similar time relative to sampling at Visit 3b	
-72 hr	6 ♀	Provision of Study Product	To occur after a min. 20 day washout period	
	7a ♂♀	Gel -72/Coitus	To occur 9 days after Visit 6	X
	7b ♀	Post-Coital Sampling	To occur ~2 hrs after coitus	

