Clinical		
 Review/update medical and menstrual history Review/update concomitant medications Perform modified physical exam Perform pelvic exam, if indicated Offer panty liners Disclose available test results Treat or prescribe treatment for UTI/RTI/STIs or refer, if indicated Record/update AEs 	
 Review/update medical history Review/update concomitant medications Perform modified physical exam Perform genital exam, if indicated Disclose available test results Treat or prescribe treatment for UTI/RTI/STIs or refer, if indicated
Behavioral/Counseling		
 Provide contraceptive counseling Provide modified HIV/STI risk reduction counseling Provide adherence counseling 	
 Provide modified HIV/STI risk reduction counseling
Laboratory	Urine	
 hCG Urine culture, if indicated Urine NAAT for GC/CT, if indicated 	
 Urine culture, if indicated Urine NAAT for GC/CT, if indicated
	Vaginal/Cervical	
 Vaginal fluid pH Rapid Trichomonas test, if indicated KOH wet mount for candidiasis, if indicated Wet mount for BV, if indicated 	
Study Product Supply		
 Provision of study product Study product use instructions Collect all used applicators/unused study product 	

Table 14: Group 2- Visit 3b: Post-Coital Sampling, Visit 5: Sampling, Visit 7b: Post-Coital Sampling

Group 2		
Group 2- Visit 3b: Post-Coital Sampling, Visit 5: Sampling, Visit 7b: Post-Coital Sampling		
Component	Female Participants	
Administrative and Regulatory	
 Provide reimbursement Schedule next visit or contact, if indicated Collect coitus visit data Eligibility to continue study participation, including continued monogamy ◇ Update locator information ◇ 	
Clinical	
 Perform pelvic exam Record/update AEs Review/update medical and menstrual history◇ Review/update concomitant medications◇ 	
Behavioral/Counseling	
 Conduct a behavioral assessment Product adherence assessment Provide contraceptive counseling◇ 	
Laboratory	Urine	
 hCG ◇
	Blood	
 PK

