7.5.1 Group 2- Visit 9: Sampling/Final Clinic Visit*

Table 15: Group 2- Visit 9: Sampling/Final Clinic Visit*

Group 2 Visit 9- Sampling/ Final Clinic Visit* Male and Female Procedures			
Component	Female Participants	Male Participants	
Administrative and Regulatory	
 Provide reimbursement Schedule next visit or contact, if indicated 	
 Provide reimbursement Schedule next visit or contact, if indicated 	
Clinical	
 Review/update medical and menstrual history Review/update concomitant medications Perform a modified physical examination Perform pelvic exam Disclose available test results, if indicated* Treat or prescribe treatment for UTI/RTI/STIs or refer, if indicated Record/update AEs 	
 Review/update medical history Review/update concomitant medications Perform a modified physical examination Perform genital exam Disclose available test results, if indicated* Treat or prescribe treatment for UTI/RTI/STIs or refer, if indicated Record/update AEs 	
Behavioral/Counseling	
 Conduct behavioral assessment Conduct acceptability assessment Provide counseling: 
 HIV pre- post- test HIV/STI risk reduction 	
 Conduct behavioral assessment Conduct acceptability assessment Provide counseling: 
 HIV pre- post- test HIV/STI risk reduction 	
Laboratory	Urine	
 hCG Urine culture, if indicated Urine NAAT for GC/CT, if indicated 	
 Urine culture, if indicated Urine NAAT for GC/CT, if indicated
	Blood	
 PK HIV-1 serology 	
 HIV-1 serology
	Vaginal/ Cervical	
 Vaginal fluid pH Rapid Trichomonas test, if indicated KOH wet mount for candidiasis, if indicated Wet mount for BV, if indicated CVL 
 PK PD Semen biomarker Vaginal and cervical biopsies 
 PK Cervical cytobrush 
 PK 	
	Rectal	
 Rectal sponge 
 PK 	
Study Product	
 Collect used applicator/unused study product (if any) 		

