7.9 Behavioral Measures

The quantitative instrument will be structured around the following topics:

- Behavioral Assessment- Sexual and other behaviors (including prohibited sexual behavior and prohibited practices)
- Product adherence (Group 2 only)
- Protocol and product acceptability

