1. Gel use, coitus, and post-coital gel use vs. endogenous activity (baseline) (PD of BAT compared to baseline CVL activity)
2. Gel use, coitus, and post-coital gel use vs. gel use (-1 hour) alone (Difference in PD of BAT compared to absence of coitus and post-coital gel)
3. Gel use, coitus, and post-coital gel use vs. gel use (-1 hour) with coitus (Difference in PD of BAT compared to absence of post-coital gel)
4. Gel use, coitus, and post-coital gel use vs. no gel use with coitus (PD of BAT compared to post-coitus endogenous activity)

Differences will be assessed with the use of the paired t-test or Wilcoxon signed-ranks test, as appropriate.

Secondary Acceptability Analysis

Descriptive statistics will be used to summarize behavioral, adherence, and acceptability data. Behavioral characteristics will be described in terms of the proportion of couples reporting sexual behaviors and practices prohibited during study participation. The adherence to product use will be described among couples in the Multiple Dose Cohort (Group 2) only, and will include assessment of the number and percentage of expected daily doses taken. The perceived acceptability of study procedures and use of the product will be described by the proportion of couples indicating that the product or procedures were found to be acceptable. The proportion of couples willing to take part in a trial of similar design in the future will be calculated. No formal testing will be performed.

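### The Group 2 evaluability window in Section 10.5 does not fit the -72 h courses, and Visit 9 has no product adherence assessment

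*Protocol*

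**What the plan says.** **Evaluability.** Section 10.5 sets three conditions for an evaluable couple, all of which must hold. The one on dosing reads "In Group 2, gel has been used daily at least 5 of the 7 days prior to the study visits". More than 20 couples may be enrolled per group until 20 are evaluable.

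**Dosing calendar.** Section 6.2.2 gives each Group 2 course seven daily doses, the first in the clinic.
- -1 h courses: doses 2-6 are taken at home and dose 7 on the day of the visit. Table 10 (Section 7.4) times Visit 3a as "To occur 6 days after Visit 2".
- -72 h courses: doses 2-7 are taken at home. Table 10 times Visit 7a as "To occur 9 days after Visit 6". For the last course, Section 6.2.2 says "The final dose of gel should be administered approximately 72 hours prior to Visit 9/Final (Sampling").

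**Adherence data.** Table 14 (Visits 3b, 5 and 7b) lists "Product adherence assessment", and Appendix II marks the same three visits. Table 15 does not list it for Visit 9, and the Visit 9 cell in Appendix II is empty. Visit 9 does have behavioral and acceptability assessments and the line "Collect used applicator/unused study product (if any"). Section 7.9 names "Product adherence (Group 2 only") as a topic of its own, apart from the behavioral assessment. Section 10.6.2 promises an adherence summary for Group 2 that "will include assessment of the number and percentage of expected daily doses taken".

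**The concern.** The evaluability rule counts calendar days back from the visit, while the courses are defined by doses. The two agree only when dosing runs up to the visit. In the -72 h courses the plan itself leaves two days (7 and 8) without gel, and those days use up part of the window. The same sentence then sets a stricter standard for two of the four courses, and a site or statistician applying it as written would replace couples who dosed well.

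The missing assessment concerns the visit that closes the fourth course. Visit 9 is the gel/no-coitus visit at -72 h, so its drug concentrations form the denominator of the percentage change defined in Section 10.6.2. The matching numerator visit, 7b, has the assessment. If dosing differed between the two courses, the adherence record would be thinner on one side of the ratio.

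**Working it through.** **The plan's own figure.** Table 18 gives power 0.807 for N = 20, a 25% difference and SD 0.375. A paired t-test with noncentrality (0.25/0.375) × √20 = 2.98 and 19 degrees of freedom gives 0.807. Two-sided alpha 0.05 is assumed, because Section 10.4 does not state it. The figure reproduces and is not in dispute; it matters here only because it presumes 20 evaluable couples.

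**Which doses the window holds.** Dose k falls on day k - 1. For a visit on day v, the seven days before it are days v - 7 to v - 1.

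| Course | Visit day | Window | Doses inside | Misses allowed by 5 of 7 days |
|---|---|---|---|---|
| -1 h (Visits 3a, 5) | 6 | -1 to 5 | 1-6 | 1 |
| -72 h (Visits 7a, 9) | 9 | 2 to 8 | 3-7 | 0 |

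Visit 9 is on day 9 because dose 7 is on day 6 and the visit follows about 72 h later. If the visit day is counted as one of the seven, the -1 h window (days 0-6) holds doses 1-7 and allows two misses. The -72 h window (days 3-9) then holds only doses 4-7, so the rule could not be met.

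**One missed home dose.**
- -72 h: the miss can be any of doses 2-7. Missing 3, 4, 5, 6 or 7 leaves four doses in the window and fails; missing dose 2 does not. That is 5 of 6 patterns.
- -1 h: the miss can be any of doses 2-6. Five of the six doses in the window remain, so 0 of 5 patterns fail.
- If the rule is 5 of the 7 doses, a single miss never fails either course.

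**Illustration under assumed adherence.** The protocol gives no expected adherence for this trial. Take 94% per dose, the self-reported figure that Section 2.5.1 gives for an earlier study of oral, vaginal and combined tenofovir, with independent misses and no make-up doses:
- -72 h, literal window: 0.94^5 = 0.734 per course; both courses 0.94^10 = 0.539.
- -1 h, literal window: 0.94^6 + 6 × 0.94^5 × 0.06 = 0.690 + 0.264 = 0.954 per course.
- 5 of 7 doses: 0.94^7 + 7 × 0.94^6 × 0.06 + 21 × 0.94^5 × 0.06^2 = 0.648 + 0.290 + 0.055 = 0.994 per course (rounded from 0.9937); both courses 0.987.

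Across per-dose adherence of 80% to 98%, both -72 h courses qualify in 10.7% to 81.7% of women under the literal window and in 72.6% to 99.9% under the dose rule.

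**Share of dosing in the Visit 9 course.** All doses: 7/28 = 25%. Home doses: 6/(5 + 5 + 6 + 6) = 6/22 = 27%.

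**The case against.** **The strict reading is probably not intended.** The protocol describes seven consecutive daily doses throughout, and Section 7.5 speaks of a 7-day regimen before Visit 7a, so 5 of the 7 dosing days is very likely what was meant. This stands. The failure patterns and percentages above describe the sentence as printed and do not forecast what sites would do. They also leave out the make-up rule in Section 6.2 and the reminders in Section 6.7, both of which reduce misses. The sentence still decides who counts as evaluable, and it should not depend on the reader correcting it.

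**Visit 9 is not without dose evidence.** This also stands. Section 6.7 has Group 2 women return used applicators at each visit after home dosing, and these are documented. Section 6.6 has unused ones counted. Table 4 fixes what is dispensed at Visit 8: one clinic dose, six home doses and one spare. Returned applicators can therefore supply a dose count for the Section 10.6.2 summary, and under a dose-based rule dates are not needed for evaluability. What they do not give is the days of use, on which the present wording depends, or the measure used in the other three courses. The protocol does not list the items of the adherence assessment, so how much more it would record is an assumption.

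**Stronger readings.** A reader might infer that the trial loses power or that the primary comparisons are compromised. The documents do not support this: non-evaluable couples can be replaced under Section 10.5, and Section 10.6.2 does not restrict its analyses to evaluable couples. A reader might also want a dose count before coitus or biopsy, with a repeat course when the limit is missed. That is an operational preference. The protocol leaves detailed procedures to the SSP Manual, Section 6.2 reschedules only when coitus does not occur, and a repeat would add 26 to 29 days (a 20-day washout plus 6 or 9 days).

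**Conclusion.** The point holds in limited form. As printed, the rule allows one miss in the -1 h courses and none among doses 3-7 in the -72 h courses, and it ignores doses 1-2 in the latter. A woman with 6 of 7 doses can be classed as non-evaluable and her couple replaced without need. This follows from the protocol's own calendar and requires no adherence assumption; only the percentages do. In addition, one of four courses, with 25% of the doses, lacks the product adherence assessment that the other three have, and it is the course behind the denominator of the -72 h comparison. The gap is an undated count where the other courses also have an assessment; it is not an absence of data. The consequence is confined to the count of evaluable couples and the completeness of the adherence data. Low priority, but worth correcting because the change is small and a missed assessment cannot be recovered later.

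**What to change.** 1. In Section 10.5, replace the Group 2 condition with: *at least 5 of the 7 doses of the course preceding each sampling visit*. This allows two misses in every course and applies equally at -1 h and -72 h.
2. Add the product adherence assessment at Visit 9, as a row in Table 15 and a mark in Appendix II.

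Cost: one reworded bullet, one table row, one mark, and one short questionnaire at a visit that already takes place. No added visits, doses or procedures, and no change to the sample size or to Section 10.6.2.
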